5.3.2. ZYN002 Phase 2 Studies

Seven Phase 2 studies have been completed in patients with epilepsy (ZYN2-CL-03, ZYN2-CL-004), osteoarthritis (OA) (ZYN2-CL-005), FXS (ZYN2-CL-009, ZYN2-CL-016), DEE (ZYN2-CL-025), and Autism Spectrum Disorder (ASD) (ZYN2-CL-030).

1. ZYN2-CL-03, a randomized, double-blind, placebo-controlled, multiple-dose study was conducted at 10 sites in Australia and 4 sites in New Zealand, to assess the efficacy and safety of ZYN002 administered as a transdermal gel to patients with focal epilepsy. The results showed ZYN002 to be safe and well tolerated with a safety profile consistent with previous studies. A total of 188 patients were randomized to receive either 195 or 390 mg/day of ZYN002 or placebo for 12 weeks. AEs were reported by 26 of 63 (41.3%) of placebo-treated patients, 31 of 63 (49.2%) of patients randomized to 195 mg/day of ZYN002 and 32 of 62 (51.6%) of patients randomized to 390 mg/day of ZYN002. For each dosing group, the majority of AEs were mild to moderate in intensity. The TEAE that occurred more frequently in patients on drug than those on placebo and occurred in at least 2% of patients included: fatigue, headache, nausea, application site dryness, anxiety, urinary tract infection, diarrhea, application site pruritus, thermal burn (secondary to seizure related accident), ataxia, oropharyngeal pain and erythema.
2. ZYN2-CL-005, a randomized, double-blind, placebo-controlled, multiple center, multiple dose study, was conducted at 10 sites in Australia, to assess the efficacy and safety of a 12 week repeat application in patients diagnosed with OA of the knee. The results showed ZYN002 to be safe and well tolerated with a safety profile consistent with previous studies. A total of 320 patients were randomized to receive ZYN002 at 250 or 500 mg/day or placebo for 12 weeks. Patients experiencing at least one treatment-emergent adverse event were similar between those on study drug (n=106, 50%) and those on placebo (n=45, 42%). The TEAEs that occurred more frequently in patients on drug than those on placebo and occurred in at least at 2% of patients included: headache, dizziness, application site dryness, application site reaction, and application site pain.

There were no clinically significant changes in vital signs, ECG, clinical laboratory results (other than eosinophilia noted above), and no reports of suicidal ideation for any patient throughout the study.

Study results for Week 51 of the extension period include:

Through Week 51 there were no clinically significant changes in vital signs, ECGs, or clinical laboratory results. Through Week 51 there were a total of 66 TEAEs reported in the study, all mild to moderate in severity, with the majority judged by the Investigator as not related to study drug. No SAEs have been reported. Gastroenteritis and upper respiratory tract infections continue to be the most commonly reported adverse events.

Efficacy Results: Eighteen patients completed the efficacy assessments through Week 12 of the study. Validated clinician- and caregiver-rated FXS scales were used to measure Baseline symptom severity and changes in symptoms between Baseline and Week 12 of the treatment period in this open-label study.

The primary endpoint was the change from Baseline to Week 12 in the total score of the ADAMS, a caregiver-rated scale. Compared to the Baseline total score, the ZYN002 treated patients had a 45.81% reduction ($p < 0.0001$) in the ADAMS Total Score. Furthermore, ZYN002 treated patients had statistically and clinically significant improvement compared to Baseline in all but one of the ADAMS subscales (i.e., Manic/Hyperactive Behavior, Social Avoidance, General Anxiety, and Compulsive Behavior) at Week 12. A significant change was not observed for the Depressed Mood subscale of the ADAMS, clinically meaningful changes were observed for all other assessments, including in the ABC-C_{FXS}, Pediatric Anxiety Rating Scale-Revised (PARS-R), and Visual Analog Scale (VAS).

Data from the extension phase of the study highlight continued gains in the primary and key secondary efficacy outcomes. The improvement observed during the initial 12-week treatment period has been sustained through 12 months. A 54.4% reduction in ADAMS

Total Score was observed between Screening and Month 12, relative to a 48.6% reduction from Screening to Week 12 (among the 12 patients enrolled through Month 12 of the extension phase). Similar changes were observed for Social Avoidance as measured by both the ADAMS (52.5% [n = 12] at Week 12 vs. 55.6% [n = 12] at Month 12) and ABC-C_{FXS} (57.9% [n = 12] at Week 12 vs. 77.2% [n = 9] at Month 12).

4. ZYN2-CL-004 was an open-label extension study to allow patients with focal epilepsy who completed ZYN2-CL-03 to continue to receive ZYN002. The primary objective was to assess the long-term safety and tolerability of ZYN002 in adult epilepsy patients over an 18-month period. The secondary objective was to evaluate efficacy in this population. Patients had to complete the 12 weeks of study treatment on protocol ZYN2-CL-03. ZYN002 was administered as a transdermal gel with all patients starting on ZYN002 at doses equal to or higher than those used in the blinded study – CBD 195 mg every 12 hours (Q12 H) (± 2 hours) (390 mg daily), with the option that after Month 1 to either increase or reduce the dose of ZYN002. The dose could be increased to 292.5 mg Q12H (± 2 hours) (585 mg daily). After one month at the 585 mg daily dose, the Investigator had the option to increase the dose to 390 mg Q12H (± 2 hours) (780 mg daily). Of the patients who completed the blinded 12-week phase, 171 (98%) enrolled in the open-label extension study. Seizure control was evaluated as a function of duration on ZYN002, regardless of initial randomization group or dose. Longer exposure to ZYN002 resulted in greater improvements in seizure frequency, with median percent change in seizures from -25% at 3 months (n=171), -40% at 6 months (n=130), -48% at 9 months (n=107), -52% at 12 months (n=94), -57% at 15 months (n=84) and -55% at 18 months (n=63).

ZYN002 was well tolerated, with excellent skin tolerability. The most common adverse events were upper respiratory tract infection (viral and bacterial; 20.4%), headache (11.7%), laceration (8.8%) and fatigue (5.8%). One patient died following the Month 15 visit; the causality is suspected Sudden Unexplained Death in Epilepsy. There have been no abnormal liver adverse events, defined as alanine aminotransferase or aspartate aminotransferase levels > 3 times the upper limit of normal.

5. ZYN2-CL-025 was an open-label study to evaluate over a 26-week treatment period, (Period A) the safety and tolerability of ZYN002 in 48 children and adolescent patients (age range 3 to <18 years) with developmental and epileptic encephalopathies (DEE). Patients weighing ≤ 25 kg received 125 mg CBD Q12H (± 2 hours), for a total daily dose of 250 mg CBD (2 sachets) for the four-week titration period. At the week four visit (Visit 4), based on Investigator discretion, the dose could remain at 250 mg CBD daily or be increased to 250 mg CBD Q12H (± 2 hours), for a total daily dose of 500 mg CBD (4 sachets) for the remaining 22 weeks of the treatment period. Patients weighing > 25 kg received 250 mg CBD Q12H (± 2 hours), for a total daily dose of 500 mg CBD (4 sachets) for the four-week titration period. At the week four visit (Visit 4), based on Investigator discretion, the dose could remain at 500 mg CBD daily or be increased to 375 mg CBD Q12H (± 2 hours), for a total daily dose 750 mg CBD (6 sachets) for the remaining 22 weeks of the treatment period. No sooner than Week 10, after evaluation of the patient's seizure diary and CBD plasma concentration from Weeks 4 and/or 6 the Investigator in conjunction with the Zynerva Medical Monitor, may determine that the patient's dose could be increased. An unscheduled visit was required in order to increase the dose. Patients taking 500 mg CBD daily may be increased to 750 mg CBD daily (6 sachets) and patients taking 750 mg CBD daily could be

increased to 1000 mg CBD (8 sachets) daily for the remainder of the treatment period. In Period B patients continued to receive ZYN002 for up to an additional 46 weeks at the same maintenance dose they were receiving at Week 26.

6. ZYN2-CL-016 was a randomized, double-blind, placebo-controlled, multiple-center study to assess the efficacy and safety of ZYN002 for the treatment of child and adolescent (age range 3 to <18 years) patients with FXS. Male and female patients with FXS were treated for 12 weeks with a two-week single-blind placebo lead-in preceding the 12-week double-blind treatment period. Approximately 204 male and female patients, ages 3 to < 18 years, were randomized 1:1 to either study drug or placebo. Randomization was stratified by gender, weight category and region. In a blinded fashion, ZYN002-treated patients who weigh ≤ 35 kg received 125 mg CBD Q12H (every 12 hours) (± 2 hours); for a total daily dose of 250 mg CBD. Patients who weighed > 35 kg received 250 mg CBD Q12H (± 2 hours); for a total daily dose of 500 mg CBD. All patients remained on their assigned dose during the 12-week treatment phase of the study.
7. ZYN2-CL-030 was an open-label study of patients aged 4 to < 18 years diagnosed with autism spectrum disorder (ASD). Treatment duration was 14 weeks with a 6-month extension. The study has concluded and is in the process of preparing results.

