11.2.1. Definition of Adverse Events

11.2.1.1. Adverse Event

An AE is an undesirable medical occurrence (sign, symptom, or diagnosis) or worsening of a pre-existing medical condition (e.g., diabetes, congestive heart failure, rheumatoid arthritis, psoriasis) that occurs at any time after signing of the ICF whether or not it is considered to be related to treatment. Worsening of an existing medical condition is when a condition present at the time of signing of the ICF (e.g., cancer, diabetes, gout) becomes more severe, more frequent, or increased in duration during the study. Hospitalizations for pretreatment conditions (e.g., elective cosmetic procedures) or surgeries that were planned before entry into the study are not considered AEs.

The Investigator is responsible for reviewing laboratory test results and determining whether an abnormal value represents for the patient a change from the time of signing of the ICF. In general, abnormal laboratory findings without clinical significance (based on the Investigator's judgment) should not be recorded as AEs. Clinically significant changes occurring after the signing of the ICF are considered AEs; however, the reported adverse event should include the underlying diagnosis or resulting clinical sequelae. Patients having clinically significant AEs will be followed until they return to normal or become stabilized.

Throughout the study, the Investigator will monitor each patient for evidence of drug intolerance and for the development of clinical and/or laboratory evidence of an adverse event. An AE assessment will be made by the Investigator on a routine basis throughout the study. All AEs which occur during the course of the study must be reported in detail on the appropriate CRF

page and on any other report form required by national law. All TEAEs must be followed to a satisfactory resolution.

All AEs will be collected from study Screening until the patient is discharged from the study.

Application site irritation scores of 1, 2, or 3 should not be recorded as AEs but will be assessed and recorded as part of the skin irritation score examinations. Skin irritation recorded with a score of '4' (as assessed by the Investigator) will be recorded as part of the skin irritation examination, and will also be recorded by the Investigator as an AE. The Investigator should report as an expedited AE (within 24 hours of assessment) to the Sponsor.

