6. GENERAL CONSIDERATIONS FOR DATA ANALYSES AND DATA HANDLING

Descriptive statistics for continuous variables include n, mean, standard deviation, standard error, median, minimum, and maximum. Descriptive statistics for categorical variables include patient counts and percentages.

6.1. Day 1

Day 1 is the date of first dose of treatment with study drug.

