8.1.6. Clinical Laboratory Tests

Clinical labs (Chemistry, Hematology, Urinalysis, and Testosterone) results at each visit and change from baseline to each visit will be summarized using descriptive statistics. In addition, clinically significant chemistry and hematology labs will be summarized. In addition, shift tables for chemistry and hematology will be prepared.

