14.3.2.7.1	Summary of Adverse Events Leading to Treatment Discontinuation by System Organ Class, Preferred Term (Period 1)	Safety Analysis Set	X
14.3.2.7.2	Summary of Adverse Events Leading to Treatment Discontinuation by System Organ Class, Preferred Term (Period 2)	Safety Analysis Set	
14.3.2.7.3	Summary of Adverse Events Leading to Treatment Discontinuation by System Organ Class, Preferred Term (Overall)	Safety Analysis Set	
14.3.2.8.1	Summary of Fatal Adverse Events by System Organ Class, Preferred Term (Period 1)	Safety Analysis Set	X
14.3.2.8.2	Summary of Fatal Adverse Events by System Organ Class, Preferred Term (Period 2)	Safety Analysis Set	
14.3.2.8.3	Summary of Fatal Adverse Events by System Organ Class, Preferred Term (Overall)	Safety Analysis Set	
14.3.2.9.1	Summary of Treatment Emergent Adverse Events by Preferred Term in Descending Order of Frequency (Period 1)	Safety Analysis Set	X
14.3.2.9.2	Summary of Treatment Emergent Adverse Events by Preferred Term in Descending Order of Frequency (Period 2)	Safety Analysis Set	
14.3.2.9.3	Summary of Treatment Emergent Adverse Events by Preferred Term in Descending Order of Frequency (Overall)	Safety Analysis Set	
14.3.3	Summary of Vital Signs by Visit	Safety Analysis Set	X
14.3.4.1	Summary of Electrocardiogram by Visit	Safety Analysis Set	X
14.3.4.2	Summary of Shifts from Baseline to Each Visit in Electrocardiogram Findings	Safety Analysis Set	X
14.3.5.1	Summary of Shifts from Baseline to each Visit in Physical Exam Findings	Safety Analysis Set	X

Summary Tables, continued

Summary Number	Title	Population	Period 1 Display
14.3.5.2	Summary of Shifts from Baseline to each Visit in Neurological Exam Findings	Safety Analysis Set	X
14.3.5.3	Summary of Shifts from Baseline to each Visit in Chemistry and Hematology	Safety Analysis Set	X
14.3.6.1.1	Summary of Chemistry Laboratory Results and Changes from Baseline to Each Visit	Safety Analysis Set	X
14.3.6.1.2	Summary of Clinically Significant Chemistry Laboratory Values	Safety Analysis Set	X
14.3.6.2.1	Summary of Hematology Laboratory Results and Changes from Baseline to Each Visit	Safety Analysis Set	X
14.3.6.2.2	Summary of Clinically Significant Hematology Laboratory Values	Safety Analysis Set	X
14.3.6.3	Summary of Urinalysis Laboratory Values	Safety Analysis Set	X
14.3.6.4	Summary of Testosterone Laboratory Values	Safety Analysis Set	X
14.3.7	Summary of Concomitant Medications by Therapeutic Class and Preferred Term	Safety Analysis Set	X

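### The SAP plans no count of patients with ALT or AST above 3 times ULN, the threshold the protocol uses to report liver safety in ZYN2-CL-004

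*Protocol*

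**What the plan says.** **The threshold.** Protocol Section 5.3.2 summarises earlier Phase 2 work. One entry reads "ZYN2-CL-004 was an open-label extension study to allow patients with focal epilepsy who completed ZYN2-CL-03 to continue to receive ZYN002", and its safety paragraph says there were "no abnormal liver adverse events, defined as alanine aminotransferase or aspartate aminotransferase levels > 3 times the upper limit of normal". This is the only place in the two documents where a multiple of ULN defines an on-treatment liver event.

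**The laboratory outputs for this trial.** SAP Section 8.1.6 plans three summaries:
- chemistry "results at each visit and change from baseline to each visit will be summarized using descriptive statistics" (Table 14.3.6.1.1). SAP Section 6 adds: "Descriptive statistics for continuous variables include n, mean, standard deviation, standard error, median, minimum, and maximum";
- "clinically significant chemistry and hematology labs will be summarized" (Table 14.3.6.1.2, titled "Summary of Clinically Significant Chemistry Laboratory Values");
- "shift tables for chemistry and hematology will be prepared" (Table 14.3.5.3).

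All three are marked for the Period 1 display. Listing 16.14.1 gives chemistry by patient, and SAP Section 9 says that all eCRF data will be listed.

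**The adverse event rule.** Under Protocol Section 11.2.1.1, "abnormal laboratory findings without clinical significance", as the investigator sees it, should in general not be recorded as adverse events.

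**The concern.** Safety and tolerability are the primary objective. For the liver, the two planned outputs that count patients or events are the adverse event tables and Table 14.3.6.1.2. Both pass through an assessment of clinical significance. For the first, the assessor is the investigator. For the second, the SAP names neither an assessor nor a numeric threshold. An ALT or AST value above 3 x ULN can therefore be missing from every event count, in an open-label trial where the investigator knows the treatment.

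What is at stake is comparability and objectivity. A report that this trial had no liver events, drawn from those two outputs, would rest on a different rule from the ZYN2-CL-004 statement in the same protocol. A reader could not put the two side by side without rebuilding the count from listings.

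**Working it through.** **Inputs**
- Threshold: ALT or AST > 3 x ULN (Protocol 5.3.2, ZYN2-CL-004).
- Patients: about 20 (Protocol 7.1 and 7.2).
- ALT and AST on treatment: Weeks 6, 14 and 38 EOS/ET (Protocol 7.6.15).
- Laboratory: samples follow local-laboratory instructions (Protocol 7.6.15), at centres in Australia and the United States (synopsis). That section also mentions a laboratory chosen for the study, so differing ULNs are possible but not certain.
- Entry limit: ALT, AST or total bilirubin at or above 2 x ULN is excluded (Protocol 8.2, criterion 4).

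The plan states no liver rate, power or precision to reproduce. The check is what each output would show for one patient whose ALT exceeds 3 x ULN and is considered not clinically significant.

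**Step 1: outputs side by side**

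| Output | Does the rise appear? | Patients above 3 x ULN counted? |
|---|---|---|
| Adverse event tables | In general no (Protocol 11.2.1.1) | No |
| Table 14.3.6.1.2 | No, if not labelled clinically significant | No |
| Table 14.3.5.3 (shifts) | Depends on categories, which are not defined | No |
| Table 14.3.6.1.1 (by visit) | Yes, if it is that visit's maximum | No |
| Listing 16.14.1 | Yes | No, would have to be built by hand |

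If the shift categories are low/normal/high, a move from normal to high appears but 1.1 x ULN and 3.5 x ULN look alike. If they follow the normal / abnormal not significant / abnormal significant pattern that SAP 8.1.3 to 8.1.5 use for ECG and examinations, the shift rests on the same assessment.

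**Step 2: mean against maximum (assumed values)**
Nineteen patients stay at 0.5 x ULN and one rises from 0.5 to 3.5 x ULN.
- Mean change = (3.5 - 0.5)/20 = 0.15 x ULN
- Visit mean = (19 x 0.5 + 3.5)/20 = 0.65 x ULN
- Median = 0.5 x ULN
- Maximum = 3.5 x ULN

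The mean and median hide the case. The planned maximum shows it.

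**Step 3: what the maximum leaves open**
- A maximum above the threshold means at least one patient, that is at least 1/20 = 5%. It does not separate 1/20 from 2/20 = 10%, and it does not say whether high maxima at Weeks 6 and 14 belong to the same child.
- If values are pooled in raw units and two laboratories have limits U1 < U2, a value V is above 3 x ULN at the first and not at the second whenever 3 x U1 < V ≤ 3 x U2. The pooled maximum then has no single multiple of ULN.
- The SAP does not say how unscheduled repeat values enter the by-visit tables.

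**Step 4: what an explicit count would give, n = 20**
- 0/20: exact upper limit 1 - 0.025^(1/20) = 16.8% (two-sided 95%), or 1 - 0.05^(1/20) = 13.9% (one-sided 95%).
- 2/20: 10%, Clopper-Pearson 95% CI 1.2% to 31.7%.
- Chance of at least one case, 1 - (1 - p)^20: 18%, 33%, 64% and 88% for assumed true rates of 1%, 2%, 5% and 10%.

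So a zero count would still leave rates up to about 17% open, which the reader should be told.

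**The case against.** The strongest reply is that nothing is concealed. By-visit minimum and maximum are planned, chemistry is listed by patient, and with about 20 patients a reader can find a large rise. If one ULN applied throughout and every value entered the table, maxima at or below 3 x ULN would settle that the count is zero. Protocol 7.6.15 also requires abnormal results to be followed to resolution, Protocol 8.4 names an adverse laboratory change as a possible reason for discontinuation, and SAP 5.1 allows ad hoc tables at the interim. All of this stands, and it is why the point is minor. It does not supply a count of patients, and it settles the zero case only under assumptions that the documents do not secure.

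Four stronger readings are tempting, and the documents do not support them:
- **That 3 x ULN is the sponsor's programme-wide definition.** It appears in one sentence about one adult epilepsy extension study. Other studies in Protocol 5.3, including the paediatric FXS study ZYN2-CL-009, are summarised by clinical significance, much as this SAP does.
- **That the plan shows liver values only as mean change, shifts and clinical significance, so that a rise would be hidden.** The maxima and Listing 16.14.1 contradict this. The rise would be uncounted, not invisible.
- **That a child entering just below 2 x ULN and rising well above 3 x ULN would show no shift.** This needs low/normal/high categories, which the SAP does not specify, and an unusual entry value that inclusion criterion 2 requires to be documented as not clinically significant.
- **That some children in the trial take valproate.** The protocol provides for such patients but does not show that any were enrolled, and epilepsy is not an entry requirement.

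It is also fair to say that the documents do not show how ZYN2-CL-004 tabulated its liver events, so exact comparability cannot be guaranteed even after the fix.

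**Conclusion.** The point holds in a limited form. No table in SAP Section 11 counts patients with ALT or AST above 3 x ULN, although the protocol uses that threshold to describe liver safety in ZYN2-CL-004. The planned event counts depend on a clinical-significance assessment, and Table 14.3.6.1.2 leaves that term undefined. A rise assessed as not significant would be traceable through maxima and the listing but absent from every event count.

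The size is 5 percentage points for each uncounted patient, taking n = 20. The documents give no ground for predicting how many such patients there would be, so this is the unit of the gap and not an estimate of bias. Two assumptions carry the argument: that some value above 3 x ULN could be assessed as not clinically significant, and that Table 14.3.6.1.2 uses the investigator's assessment, which is inferred from Protocol 11.2.1.1. The severity is minor: the study is exploratory and descriptive, and no error rate or sample size is affected.

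**What to change.** In SAP Section 8.1.6, and as a new line in Section 11 marked for the Period 1 display and repeated at the final analysis, add one by-patient table:
- for each patient, the highest post-baseline ALT and the highest post-baseline AST, from scheduled or unscheduled samples, divided by the ULN of the laboratory that reported the value;
- the number and percentage of patients with ALT or AST > 3 x ULN, with an exact (Clopper-Pearson) 95% confidence interval, whatever the clinical-significance assessment;
- as denominator, safety-set patients with at least one post-baseline value.

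A total bilirubin column is optional. The documents set a bilirubin multiple only as an entry criterion, so any reporting cut-off for it would be a new choice.

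The cost is one extra table from samples already taken. The reporting laboratory's ULN must be held with each result; the documents do not say whether Listing 16.14.1 carries reference ranges, so this needs checking. No procedure, visit or clinical rule changes.
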